4.5.2 Case validation with PCPs

We will send for a random sample of 300 potential cases a questionnaire to PCPs requesting them to send copies of all related paper-based information in order to confirm our operational definition of incident seizure. If the information from the questionnaire and medical records confirms our case definition of incident seizure in 85% of instances or greater, we will not request additional records for the remaining potential cases.

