4.5 Outcome definition and ascertainment

Free text comments will be requested before reviewing patient profiles. Information will include demographic data and all clinical information. The profiles of computer detected patients with seizure/convulsion (Table 2) identified with the initial computer search and including free-text comments, will be reviewed manually to ascertain the number of potential cases with an incident episode of seizure. All patient personal identifiers will be suppressed and information on drug use removed to allow for a blinded revision of patient profiles. The date of onset of study outcome will be used as index date. Doubtful cases will be reviewed by two MD researchers and agreement will be reached. Patients will not be retained as seizure cases if they were admitted to hospital in the month before the index date; in-patient drug exposure is not available and therefore recent exposure in these patients would be unknown. All patients meeting our operational definition of seizure (see below) will be considered potential cases.

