4.9 Statistical analysis

Incidence rate of seizure overall as well as age and sex-specific will be computed in the study cohort.

A nested case-control analysis will be performed to assess the effect of acid-suppressing drugs and potential risk factors for seizure using unconditional logistic regression. In this analysis all patients ascertained with an incident episode of seizures will be used as

cases. The control group will comprise a random sample of study cohort members, frequency-matched by calendar year (described in section 4.6). Under our study design of incidence density sampling, the odds ratio (OR) is an unbiased estimator of the incidence rate ratio (RR) (Rothman 2002).

To determine the association between study outcome and current use of PPI and H₂RA, we will run unconditional logistic regression models and compute the OR and their 95% confidence intervals (95%CI). The estimates will be adjusted for the frequency-matched variable (calendar year), age, sex, time to event and other independent risk factors described in section 4.7.

Sub-analyses will be repeated in the strata of individuals with epilepsy and individuals free of epilepsy for descriptive purposes.

Statistical analyses will be performed using Stata package version 11.0 (StataCorp LP, College Station, TX, USA).

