4.9.1 Sample size

Assuming an experience of 100,000 person-years among PPI current users, 100,000 person-years among non users of PPI and an incidence rate of seizures of 50 per 100,000 person-years among non users of PPI and a true relative risk of one, a 95% CI would extend to 1.48 if the estimated ratio is 1. We expect to accumulate larger person-time experience than mentioned above both among current users of PPI and non users.

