5. STUDY STRENGTHS AND LIMITATIONS

Strengths

A major strength of this study is that use of THIN enables analysis of an extensive sample of PPI users that is representative of the UK primary-care population, with a similar age and sex distribution to those in the national population supporting a broad external validity of our findings and generalizability. Also, we will analyze the risk in another drug class (H₂RA) that share similar treatment indication than PPI to verify the specificity of the results. Validation of the outcome with the PCP will help to reduce the extent of outcome misclassification when working with automated databases.

Limitations

A potential limitation of the study is that acid suppressing drug use could be misclassified in some instances. For example, the recording of a PPI prescription in THIN does not necessarily mean that the patient actually took the medication, although it is likely that patients with repeating prescriptions do take their medication as there is a prescription almost every month. Also, lack of recording of OTC acid suppressing drugs is another source of misclassification (PPI available as OTC June 2009 on UK market). This misclassification of drug exposure will most likely be non-differential and thus will bias the effect estimates towards the null. Therefore, it should be noted that to the extent

such misclassification occurs in our study population, our effect estimates will tend to underestimate the true risk. As with any medication, PPI users might differ from non-users in a number of characteristics, such as treatment indication, severity of the treatment indication, co-morbidity, etc. Like in all observational studies, there is always the possibility for some remaining confounding not amenable to adjust after all our efforts in the design and analyses.

Outcome missclassification of seizure will be substantially reduced with our two step validation process: first obtaining free text comments for the review of the patient profiles and second the direct validation with the PCP. The extent of recording of comorbidity, medication use and life style habits in THIN will help to minimize as much as possible potential confounding by any these variables.

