6.3 Study reporting

The final analyses and study report is estimated to be delivered within 20 months of external approval from ethic committee assuming 3 months for anonymization of free text comments by the external provider of THIN data (AIS) and 3-4 months for obtaining questionnaires from PCPs, aiming at high response rate (around 80-90%) with anonymization of all information. At least one manuscript based on the findings of this project will be submitted for publication to a peer-reviewed journal.

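### The 85% confirmation rule works only as a stop/go gate, so at the threshold false positives left in the case count overstate seizure incidence by up to about 18%; the effect on the odds ratios is secondary

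*Protocol*

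**What the plan says.** Case ascertainment has two steps. In section 4.5, all computer-detected profiles are reviewed manually with free text, with "information on drug use removed to allow for a blinded revision of patient profiles"; doubtful cases go to two physicians. Patients who meet the operational definition become potential cases.

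The second step is in section 4.5.2: "We will send for a random sample of 300 potential cases a questionnaire to PCPs". If the definition is confirmed "in 85% of instances or greater, we will not request additional records for the remaining potential cases". Section 6.3 plans the questionnaires "aiming at high response rate (around 80-90%) with anonymization of all information". Table 3 has the investigator assign case status after reviewing the returned material.

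For the analysis, section 4.9 states: "Incidence rate of seizure overall as well as age and sex-specific will be computed in the study cohort". On the case-control part it says: "In this analysis all patients ascertained with an incident episode of seizures will be used as" cases. Section 5 describes outcome misclassification as substantially reduced by two steps, "first obtaining free text comments for the review of the patient profiles and second the direct validation with the PCP". The protocol does not say how the observed confirmation proportion enters an incidence rate, an odds ratio or a confidence interval.

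**The concern.** The 300 are drawn from cases that have already passed the manual review. A confirmation rate of 85% therefore means that about 15% of such cases fail the operational definition after the first step. Once the gate is passed, the unsampled cases keep that error, and each counts as one event.

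Incidence is the first study objective. False positives in its numerator bias it upwards, and the bias does not shrink as the study grows. With 1,000 cases, the half-width of a Poisson 95% interval is about 1.96/√1,000 = 6%, so an excess of 13% would lie outside an interval that looks precise. For the second objective, false cases whose exposure resembles that of controls would weaken a raised odds ratio, which is the unwelcome direction in a safety study.

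**Working it through.** **The plan's own figure.** Section 4.9.1: "Assuming an experience of 100,000 person-years among PPI current users, 100,000 person-years among non users of PPI", at 50 seizures per 100,000 person-years and a rate ratio of 1. That gives 50 events per group and an upper limit of exp(1.96 × √(1/50 + 1/50)) = 1.48, as stated. The calculation treats every event as true.

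**Inputs.** Threshold 0.85 and sample 300 (section 4.5.2). Response 80–90%, so 240–270 returns, with 255 as the midpoint (section 6.3). Reference rate 50 per 100,000 (section 4.9.1). The number of potential cases, N, is not given; the values below are assumptions.

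**Incidence, no false case removed.** Overstatement = 1/PPV − 1.
- PPV 0.85: 17.6%, for example 50/0.85 = 58.8 instead of 50 per 100,000.
- PPV 0.90: 11.1%.
- PPV 0.95: 5.3%.

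**Incidence, refuted sampled cases dropped.** With m returns, the ratio of counted to true cases is [0.85m + (N − m)]/(0.85N).
- m = 255, N = 1,000: (216.75 + 745)/850 = 1.13.
- m = 255, N = 3,500: (216.75 + 3,245)/2,975 = 1.16.
- m = 300, N = 500: (255 + 200)/425 = 1.07.
- All cases validated: 1.00.

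**Sampling error of the gate.** The 85% is an observed proportion.
- 255 of 300 confirmed: exact 95% CI 80.4–88.8%, an overstatement of 12.6–24.3% if no false case is removed.
- 204 of 240 confirmed: exact 95% CI 79.8–89.3%, an overstatement of 12.0–25.2%.
- A true PPV of 0.82 still passes with probability of about 0.10 (300 returns) to 0.13 (240 returns).

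**Odds ratio.** Exposure probability in the case set = 0.85 × that of true cases + 0.15 × that of false cases, with all false cases retained.
- False cases exposed like controls, control exposure odds 0.05–0.20 (assumed): a true 1.0 stays 1.0, 1.5 becomes 1.42, and 2.0 becomes 1.83–1.84. Worked at odds 0.10 for a true 1.5: 0.85 × 0.1304 + 0.15 × 0.0909 = 0.1245; odds 0.1422; ratio 1.42.
- False cases exposed differently from controls, control exposure 5–20% (assumed): a null odds ratio moves to about 1.07 if their own exposure odds ratio is 1.5, to 1.13–1.14 if it is 2, and to 0.92 if it is 0.5.

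**Check of the remedy.** N = 1,000, m = 255: 216.75 + 0.85 × 745 = 850, which is the true count at PPV 0.85.

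**The case against.** Several points on the other side are right and set the limits of this finding.

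- A reader might infer that the remaining cases are accepted unchecked. They are not: each has passed the blinded review in section 4.5. Section 5 claims reduction of misclassification, not elimination, so it is not contradicted.
- A reader might infer that 15% of the whole case set is false. Table 3 implies that refuted sampled cases lose case status, so the share applies to the cases not validated.
- The size depends on N. The planning figures in section 4.9.1 imply only 100 events, although that section expects more person-time. On the other hand, a rule about remaining cases makes sense only if there are more than 300.
- A reader might infer that the odds ratios are generally distorted. The documents do not support this. Blinded review makes differential error less likely, a null odds ratio is unchanged when false cases are exposed like controls, and the shift from 1.5 to 1.42 is small beside the planned upper limit of 1.48 around an estimate of 1. An unconfirmed case may also be a real seizure without referral or admission.
- Only false positives are counted. Patients admitted in the month before the index date are not retained, and uncoded events are missed. The protocol gives no sensitivity, so the net error against all seizures is unknown.
- A correction might stand in an SAP that is not shown. However, the stopping rule, the definition of the case set and the assurance in section 5 are protocol text, and followed as written they leave the PPV unused.

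**Conclusion.** The point holds for incidence. The protocol sets a tolerated and measurable upward error in a stated objective and does not use the measurement. At the threshold, the overstatement of operationally defined incidence is up to 17.6% as a limiting point value. With refuted sampled cases dropped and 255 returns, it is about 13% for 1,000 and 16% for 3,500 potential cases, both numbers assumed. It is smaller at a higher PPV and zero if every case is validated. The 17.6% is neither a forecast nor a strict ceiling, because the PPV is itself estimated.

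For the odds ratios the consequence is secondary: modest attenuation of a raised value if false cases are exposed like controls, and none at the null. This is a cheap improvement, not a flaw that undermines the study.

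**What to change.** Keep the 85% gate, and make these changes:

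1. Section 4.5.2: state that sampled cases refuted by the returned information are removed from the case set.
2. Section 4.9: report the incidence rates also with unsampled and unreturned cases weighted by the observed PPV, with its sampling error carried into the 95% CI, for example by bootstrap.
3. Section 4.9: add a sensitivity analysis of the PPI and H₂RA odds ratios using the overall PPV. Do not plan exposure-specific PPVs unless numbers are adequate. At exposure odds of 0.05–0.20 (assumed), 255 returns would include only about 12–43 current users, and 10 of 12 confirmed has an exact 95% CI of about 52–98%.
4. Section 5: say that direct PCP validation covers only the sample when the gate is passed.

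The cost is protocol or SAP wording and a small extra analysis of questionnaires already planned. The downside is a somewhat wider interval and a lower reported incidence. Weighting by the PPV corrects false positives only, so the unweighted rates should remain in the report.

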4.6 Selection of Controls

A random series of controls, calendar-year-frequency matched to seizure cases will be sampled from the pooled study cohorts. This will be done by generating a random date within the study period for each study member. If the random date for a study member is included in the follow-up period, that person will be marked as an eligible control and the random date will be used as their index date. This method of selection of controls in nested case-control studies is known as "incidence density" sampling. The final size of the control sample will be determined by being at least four times the size of the final list of cases and be a round number.

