Drugs associated with the development of convulsion/seizure include cocaine, other CNS stimulants, cyclosporine, tacrolimus, pentylenetetrazole, picrotoxin, strychnine. There are also drugs, described to lower seizure threshold such as aminophylline, antidepressants, sedating antihistamines, antimalarial drugs, some antipsychotics (eg, clozapine), buspirone, fluoroquinolones, theophylline (Ruffman et al 2006). In a study from 1977, seizures were recorded in less than 1% of 32 812 consecutive patients prospectively monitored for drug toxicity in selected medical wards (Porter et Jick 1977).

Antiepileptic medications are a heterogeneous pharmacologic class characterized by various chemical structures and postulated mechanisms of actions (Paterno et al, 2010). The main therapeutic applications of antiepileptics include epilepsy, bipolar disorder, depression, neuralgia, and migraine (Ettinger et al, 2007). Antiepileptic drugs (AEDs) are among the most commonly prescribed centrally active agents. In a survey, carried out in a Danish County, 1.1% of the studied people received AEDs. The use of these drugs increased with increasing age (Rochat et al 2001).

Proton pump inhibitors (PPIs) and H₂-receptor antagonists (H₂RAs) are widely prescribed acid-suppressive medications that in general have good safety profiles (Yang and Metz, 2010). AstraZeneca has received spontaneous reports of convulsion/seizure reported in patients taking esomeprazole and omeprazole. As commonly observed in postmarketing reports, information with regard to possible underlying cause, concomitant medication and potentially contributing factors were limited. In AstraZeneca placebo-controlled studies comprising esomeprazole or omeprazole no reports of convulsion/ seizure in patients given PPIs were found.

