3. STUDY OBJECTIVES

- To estimate the incidence of seizure in the general population and stratified by epilepsy status
- To estimate the relative risk of seizure associated with use of PPI and H₂RA and stratified by epilepsy status.

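### One pooled control series, matched on calendar year only, will very probably leave fewer controls than cases in the epilepsy stratum, so its promised relative risk will be avoidably imprecise

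*Protocol*

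**What the plan says.** Section 3 lists as an objective: "To estimate the relative risk of seizure associated with use of PPI and H₂RA and stratified by epilepsy status". Section 4.9 plans the matching analysis, with a qualifier that neither section 3 nor the synopsis carries: "Sub-analyses will be repeated in the strata of individuals with epilepsy and individuals free of epilepsy for descriptive purposes".

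Section 4.6 provides the controls. "A random series of controls, calendar-year-frequency matched to seizure cases will be sampled from the pooled study cohorts". Eligibility follows from a random date: "If the random date for a study member is included in the follow-up period, that person will be marked as an eligible control". The total is set as "at least four times the size of the final list of cases and be a round number". No quota or separate draw is given for people with epilepsy.

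Section 4.5.1 also accepts a broader case definition for the epilepsy sub-analysis, one that requires neither referral nor admission. Section 4.6 does not say whether the cases this adds count towards the control total. Section 4.9.1 states precision for the whole cohort only.

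**The concern.** A random-date draw yields controls with epilepsy in proportion to their person-time. The only figure in the protocol that bears on that proportion is in section 2, from a survey in a Danish county: "1.1% of the studied people received AEDs". That figure covers antiepileptic use for every indication. Cases are a different matter: people with epilepsy are, by the definition quoted in section 2, those with a lasting tendency to seizures, and the broader definition in 4.5.1 adds more of them.

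The planned ratio is therefore lost exactly where a stratified relative risk is promised. At stake is the width of the epilepsy-stratum interval for current PPI use. H2RA use, dose and duration (section 4.8) divide the same few exposed controls further. An analysis plan cannot repair this later, because it cannot supply controls that were never sampled.

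**Working it through.** **The plan's own figure.** Section 4.9.1 assumes 100,000 person-years in each of two groups and 50 seizures per 100,000, so 50 and 50 events. SE(log RR) = sqrt(1/50 + 1/50) = 0.20 and the upper limit is exp(1.96 × 0.20) = 1.48. This reproduces. It has no counterpart for the epilepsy stratum.

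**Controls per case in the stratum.** Let N be total cases, p the epilepsy share of person-time and s the epilepsy share of cases. At 4:1 overall there are 4Np controls and Ns cases with epilepsy, so the ratio is 4p/s. Because s/p is the seizure rate in epilepsy divided by the overall rate, the ratio equals 4 × (overall rate / rate in epilepsy), whatever N is. It drops below 1 once the rate in epilepsy exceeds four times the overall rate, which is 4 × 50 = 200 per 100,000 person-years at the planning rate.

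With p = 1.1%:
- s = 5%: 0.044/0.05 = 0.88
- s = 10%: 0.044/0.10 = 0.44
- s = 30%: 0.044/0.30 = 0.15
- s = 50%: 0.044/0.50 = 0.09

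Over p from 0.5% to 2% and s from 10% to 50% the range is 0.04 to 0.80. Of the combinations tried, only p = 2% with s = 5% exceeds 1 (0.08/0.05 = 1.6).

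**Precision at a true odds ratio of 1.** With nc cases and nk controls in the stratum and current PPI use q, SE(log OR) = sqrt(1/(nc·q) + 1/(nc(1−q)) + 1/(nk·q) + 1/(nk(1−q))). The CI factor is exp(1.96 × SE), the number by which the estimate is multiplied and divided.

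Example: N = 1,000, p = 1.1%, s = 10%, q = 5% gives nc = 100 and nk = 44. SE = sqrt(1/5 + 1/95 + 1/2.2 + 1/41.8) = 0.830, factor 5.09. With nk = 400, SE = sqrt(1/5 + 1/95 + 1/20 + 1/380) = 0.513, factor 2.73.

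Assumptions for the table, none of them stated in the protocol for this cohort: p = 1.1%, s = 10-30%, q = 5-10%.

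| Total cases | Epilepsy cases | Epilepsy controls as planned | Exposed among them | CI factor as planned | CI factor at 4:1 in stratum |
|---|---|---|---|---|---|
| 500 | 50-150 | 22 | 1.1-2.2 | 4.4-10.0 | 1.8-4.2 |
| 1,000 | 100-300 | 44 | 2.2-4.4 | 2.9-5.1 | 1.5-2.7 |
| 2,000 | 200-600 | 88 | 4.4-8.8 | 2.1-3.2 | 1.35-2.0 |
| 4,000 | 400-1,200 | 176 | 8.8-17.6 | 1.7-2.3 | 1.2-1.65 |
| 6,000 | 600-1,800 | 264 | 13.2-26.4 | 1.5-1.9 | 1.2-1.5 |

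At the 100 events of section 4.9.1 there would be about 4 epilepsy controls and fewer than one exposed, so no usable estimate; the protocol expects more person-time than that.

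**Sensitivity to p.** At 1,000 cases the planned factor is 4.5-9.1 for p = 0.5% and 2.3-3.9 for p = 2%. At 6,000 cases it is 1.9-2.5 and 1.4-1.7.

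All factors are unadjusted. Adjusting for the long covariate list in section 4.7 with so few stratum controls would widen them.

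**The case against.** The strongest reply is that the size of the problem rests on figures that the protocol does not give. This stands. A reader might infer that the stratum estimate will be close to uninformative, or that the objective cannot be met. That holds up to roughly 1,000 cases. At the planning rate, 1,000 cases need only 1,000/0.0005 = 2 million person-years, and the database holds more than 3 million patients over a seven-year window. The eligible fraction is unknown, but several thousand cases are possible, and at 4,000-6,000 the factor is about 1.5-2.3: imprecise, yet usable.

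The 1.1% is also only a proxy. Section 4.7 lists epilepsy as a comorbidity ascertained before the index date, so untreated epilepsy may count and p may be higher. Under the strict case definition, people with epilepsy who are not re-referred drop out, which lowers s. Both soften the imbalance, but over the ranges tried they rarely remove it.

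Two further replies carry less weight. The 4:1 ratio is a floor, so more controls are allowed. But reaching 4:1 in the stratum through the pooled draw would take 4s/p = 0.4/0.011 to 1.2/0.011, about 36 to 109 controls per case overall, and nothing in 4.6 points to that. The descriptive label in 4.9 lowers the claim made for the result, but it does not add controls, and section 3 states the objective without it.

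A reader might also infer that both stratified objectives suffer. They do not. The other one, "To estimate the incidence of seizure in the general population and stratified by epilepsy status", uses cohort person-time and does not depend on control sampling.

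**Conclusion.** The concern holds as a matter of efficiency. The epilepsy stratum will very probably have fewer controls than cases; this needs only a seizure rate in epilepsy above four times the overall rate. How much precision is lost depends on the case total. Under the stated assumptions, four controls per case inside the stratum would cut the CI factor from about 2.9-5.1 to 1.5-2.7 at 1,000 cases, and from about 1.5-1.9 to 1.2-1.5 at 6,000. Matching the whole-cohort limit of 1.48 within the stratum under the present sampling would need about 7,200-17,200 total cases.

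The sampling scheme introduces no bias, and the whole-cohort odds ratio is unaffected. This is a recommended improvement, not a defect that must be cured before the study can proceed.

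**What to change.** In section 4.6, keep the main control series as it is and add a supplementary incidence-density series drawn from the person-time of cohort members with epilepsy. Match it on calendar year, set it at no fewer than four controls per epilepsy case under both the strict and the broader definition of 4.5.1, and use it only for the epilepsy sub-analysis. Since the strict cases are a subset of the broader ones, one series sized on the broader count serves both. Numbers should not be a constraint: 1.1% of 3 million is about 33,000 people before exclusions, against 4 × 1,800 = 7,200 controls at the largest epilepsy case count in the table.

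The cost is a second database draw and a separate analysis set, with no extra record review, because only cases are validated. The change has to be made before controls are selected.

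Matching the pooled series on epilepsy status is the less attractive route. It would give up the main effect of epilepsy, which sections 4.7 and 4.9 list among the risk factors to be assessed. It would also help to state the expected stratum numbers and precision in 4.9.1, and to use the same status for this analysis in section 3 and section 4.9.
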